We will address these issues using a 4 site feasibility RCT to compare standardised PI (incorporating CBT+FI) to treatment with APs and a combined treatment (PI+APs) in 90 adolescents with FEP. This will inform the feasibility and design of a future definitive, pragmatic clinical and cost-effectiveness trial. Randomisation using permuted blocks of variable length will be stratified by family contact (i.e. if they are living with their family) and site. Assessors will be blind to allocation. Nested qualitative studies will identify key themes about the acceptability of treatments in adolescents with FEP, as well as experiences of trial involvement, including wanted and unwanted effects. Gauging the opinions of parents and clinicians, in addition to young people themselves, is crucial to assess feasibility of a full definitive RCT.

Aims and objectives:

Our primary aim is to determine whether it is feasible to conduct a study to examine the effectiveness of psychological therapy, antipsychotic medication or a combination of the two, in adolescents with first episode psychosis.

Specific objectives are to assess, under randomised conditions:

 The proportion of eligible people clinicians are willing to refer, the proportion of eligible people willing to participate and the proportion of participants who comply with their allocation

- The drop-out rate, and the proportion of clinicians willing to refer to the trial
- The characteristics of trial participants to clarify selection criteria
- The appropriateness and integrity of treatment protocols and the feasibility and acceptability of the interventions to participants, parents and referring clinicians
- The randomisation procedures
- The relevance and validity of the measures to assess effectiveness, safety and acceptability in a subsequent definitive trial

We will also:

- Estimate sample size parameters to inform the design of a definitive trial Clarify training/supervision needs for delivering interventions/assessments
- Finalise treatment manuals and outcome measures
- Assess the possibility for economies of scale and monitor time use of the research assistants

Research Plan:

Study Design

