It would be unethical to restrict the therapeutic options of the clinical teams participating. Our approach will, therefore, be primarily to record the use of all other medication and psychological therapies, document details of dosage, and ensure the follow-up of all

randomised participants, irrespective of the interventions that they subsequently receive. We will collect participant self-report on the use of medication and psychological therapies and in addition, research assistants will screen the medical records for this information at the end of the study. This will allow us to determine the possibility for economies of scale for data collection. All participants will be eligible to receive medications other than APs (i.e. benzodiazepines, antidepressants etc.) and psychological therapies other than CBT or FI.

Health technologies being assessed:

The PI intervention will use a specific cognitive model (21) to guide both CBT and family intervention. We have used this model successfully in 5 clinical trials with young people with psychosis, and have had successful clinical results and positive feedback regarding acceptability and utility from several nested qualitative studies with the trial participants. CBT is required because there is evidence that it is the most suitable and effective psychosocial intervention to help resolve symptoms, which led to it being NICE recommended in CG155. An element of family intervention is required for two reasons: i) given the developmental stage that our participants are at (adolescence, aged 14-18), it would be inappropriate to work with the participant in isolation from their parents, who are key stakeholders in the health and wellbeing of their child; ii) family intervention is recommended by NICE in CG155 on the basis of ability to prevent relapse. The combination of developmentally-adapted CBT and family intervention represent the best available psychosocial interventions for adolescents with first episode psychosis, as outlined in CG155; therefore, this combination is the appropriate comparator in a head-to-head comparison with pharmacological interventions.

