Comparator conditions are antipsychotic medication (APs) and a combined treatment (APs plus PI). The APs will be selected by the clinician from those commonly used in the treatment of young people with psychosis, with dosages within recommended limits; the responsible consultant psychiatrists will choose the individual AP. The choice of antipsychotic medication should be made jointly with the young person and their parents or carers, and healthcare professionals. Age-appropriate information will be provided by prescribers to facilitate this and the likely benefits and possible side effects of each drug will be discussed. The psychiatrists will initiate the first dose of AP as soon as possible and will be encouraged to keep patients on their AP for a minimum of 12 weeks, and preferably for 26 weeks; however, they will be free to change dose and type of antipsychotic in response to monitoring of efficacy and adverse effects, which is consistent with current NICE guidelines. Treatment with antipsychotic medication will be considered an explicit individual therapeutic trial. This will incorporate: recording the side effects the child or young person is most and least willing to tolerate; the indications and expected benefits and risks of oral antipsychotic medication; the expected time for a change in symptoms and appearance of side effects. At the start of treatment, we will encourage clinicians to prescribe a dose at the lower end of the licensed range. For drugs not licensed for children and young people this would be below the lower end of the licensed range for adults. This will be followed by slow titration upwards within the dose range given in the British national formulary (BNF), the British national formulary for children (BNFC) or the SPC. We will also ask clinicians at each clinical review to record the rationale for continuing, changing or stopping medication, and the effects of such changes. Prescribers will be encouraged to adhere to NICE Guidance parameters about AP choice, dosage and titration. Prescribing information will be recorded for each participant in a clinical form. In order to determine economies from scale we will collect this data in two formats: participant self-report, which will be completed online via the Clinical Trial Unit (CHaRT) secure web-based platform (in order to protect the blind) and via researcher medical record screening. The above represents good practice and NICE guidance; in order to support adherence to these recommendations we will provide prescribers with access to the NICE elearning tool that accompanies CG155 on prescribing and monitoring APs and the NICE audit tool based on CG155 describing recommended APs, titration and effective dose ranges, monitoring and rules for dose escalation and AP cessation and/or switching. The aim is to ensure that AP prescribing in the trial adheres to current best practice guidelines. In addition, throughout the recruitment phase of the trial, the psychiatrist co-applicants will meet with local psychiatrists at their sites to discuss the trial, inclusion criteria, documentation and any emergent concerns.

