Child & Adolescent Mental Health Services (CAMHS) or Early Intervention Services (EIS) at 4 UK sites (Manchester, Birmingham, Oxford and Sussex)

Sampling and Feasibility of recruitment

We confidently anticipate that we can achieve the recruitment targets by sampling across early intervention, CAMHS and youth services in our 4 sites. These research sites have successfully collaborated before and participated in a series of related studies. The staff and managers involved in our sites are highly motivated to participate and are familiar with recruiting participants into research trials. The sites have extensive existing links with agencies in primary care, child and adolescent, and adult mental health services, with established referral pathways for recruiting these types of cases into both clinical services and research. The sites have existing services which already receive referrals of adolescent cases with FEP at a rate of around 100 per year (total 400 per year in all centres); it should be noted that all sites cover a large geographical area, and all have possibilities to extend into adjacent mental health NHS Trusts if necessary. Data from related trials suggests that approximately 50% of these existing referrals are likely to meet criteria for the present project. This should facilitate the present study.

We aim to recruit 90 CYP across the 3 conditions (30 per condition) over the 15-month recruitment period. Assuming a recruitment rate of approximately 1.5 cases per month per site, this will be sufficient to recruit to target over the feasibility trial. We are currently randomising 3 per month in a single site RCT comparing APs, CBT and both in adults with psychosis and local audits suggest >100 eligible adolescents per site (we anticipate a lower recruitment rate than our adult trial given the lower incidence and prevalence of adolescent FEP). We will audit reasons among those who decline participation as a learning opportunity to improve recruitment within this feasibility study and for any subsequent trial.

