We will report our feasibility results (recruitment, retention, adherence) overall, in order to inform decisions about the viability of a future definitive trial. However, we will also report our descriptive results and 95% confidence intervals on outcome measures by group. To inform a phase III trial we will conduct the following analysis to ensure the data conforms to the assumptions of the tests which will be conducted at that stage: measures proposed as the primary (PANSS) and secondary outcomes (QPR) for the phase III study will be analysed using analysis of repeated measures using a mixed effects model to take into account the discrete timing of the follow-up assessments. The presentation of the analysis will focus on point estimates and associated 95% confidence intervals rather than statistical significance (pvalues). The sensitivities of all treatment effect estimates to missing outcome data arising from drop-out will be examined. Further analysis will assess the correlations of each measure across all time points and the variation within the proposed outcome measure (mean and standard deviation) to inform a definitive sample size calculation for a phase III trial. The primary statistical support will be provided by [name] and [name] from CHaRT. Secondary, exploratory analyses will involve investigation of treatment effects and possible mediation mechanisms using appropriate statistical methods (37); statistical support for this aspect will be provided by [name]. At the end of this we will be in a position to design a definitive phase III trial with which to evaluate our intervention rigorously. All statistical analyses will be pre-specified in a comprehensive Statistical Analysis Plan which will be agreed

with TSC and DMC. The results of the trial will be presented following the standard CONSORT recommendations.

We will measure within trial and also explore the literature regarding the possible effects of clustering by therapist and site. We anticipate that the chance of clustering regarding drug outcomes will be negligible, given we are expecting prescribing to follow CG155 NICE guidance, although we will measure this in case of significant differences in prescribing practices between sites. We will adjust for site in analyses (therapist will be nested within site) and examine intraclass correlation coefficients to inform a plan for managing any such impact on design and analysis of a definitive trial.

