unmeasured confounders (hidden confounding) using instrumental variable-based methods, specifically analyses based on principal stratification (37).

Measurement of feasibility success criteria:

At 24 months the TSC and DMC will check criteria for progression to a full trial and make recommendations to proceed to a full trial or not. The criteria will be:

- i) Recruitment ≥80% of planned (green), recruitment within 79 -60% of planned (amber), recruitment < 60% of planned (red).
- ii) Retention of participants within the study with baseline and outcome assessments at primary end point (6 months, end of treatment) ≥80% of primary outcome completed (green), 79 -60% of primary outcome completed (red).
- iii) Satisfactory delivery of adherent therapy to ≥80% of groups receiving PI (green), 79-60% of groups receiving PI (amber), < 60% of groups receiving PI (red). Satisfactory delivery of adherent therapy will be operationalised as attending 6 or more sessions of CBT.
- iv) Satisfactory delivery of antipsychotic medication to ≥80% of groups receiving AP (green), 79-60% of groups receiving AP (amber), < 60% of groups receiving AP (red). Satisfactory delivery of antipsychotic medication will be operationalised as any exposure of AP for 6 consecutive weeks (this would include a dose below BNF lower limits given this is a frequent clinical practice for people of this age and the drugs are licensed for adults) records.

Plan of investigation and timetable:

Prior to start of the study: Preparations to be made before the beginning of the study will be a) obtaining ethics and research governance approvals (b) publicising the study to senior managers, clinicians and service users in the sites participating in the study (c) recruiting the members of staff beginning with appointing the trial manager ([name], a co-applicant) who will participate in the recruitment of other staff (d) trial therapists will be identified before the start of the study and attend a series of pre-study workshops discussing client information and undertaking their own pilot cases using the therapy manual.

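### The progression criteria pool retention and treatment delivery across arms and ignore receipt of the non-allocated treatment, so all can be green while a monotherapy arm has not been shown to be feasible

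*Protocol*

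**What the plan says.** Protocol, Data analysis: "We will report our feasibility results (recruitment, retention, adherence) overall, in order to inform decisions about the viability of a future definitive trial". The next sentence turns to what is given by group, and lists descriptive results and 95% confidence intervals on outcome measures.

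Protocol, Measurement of feasibility success criteria:

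- Criterion ii (retention at 6 months) is green at 80% or more and names no arm.
- Criterion iii (therapy) is a percentage of the groups receiving PI, with this definition: "Satisfactory delivery of adherent therapy will be operationalised as attending 6 or more sessions of CBT".
- Criterion iv (medication) reads "Satisfactory delivery of antipsychotic medication to ≥80% of groups receiving AP (green" and is met by any AP exposure lasting 6 consecutive weeks.

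PI is given in the PI-alone and combined arms, and AP in the AP-alone and combined arms, so criteria iii and iv each span two arms. No criterion refers to receipt of the treatment that was not allocated.

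Protocol, Aims and objectives, lists among the things to be assessed "the proportion of participants who comply with their allocation". The Rationale names compliance with allocated treatment as a key uncertainty, and non-inferiority of the monotherapies as one of the possible definitive questions. The Summary and Procedures for deterioration both provide for monotherapy participants to transfer to combined treatment.

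**The concern.** Whether PI alone can be compared with APs alone depends on two things in each monotherapy arm: participants must be followed to 6 months, and they must largely stay on one treatment. The criteria measure neither by arm. A pooled percentage lets a strong arm make up for a weak one. A delivery measure that counts only the allocated treatment cannot separate a monotherapy arm that stayed monotherapy from one that became combined treatment.

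Differential loss and cross-over are also what would most damage a later comparison of the monotherapies. Loss that differs by arm can bias it. Cross-over into combined treatment makes the arms alike, which is particularly awkward in a non-inferiority trial because it favours a finding of no difference. A pilot should show how large these problems are before the decision to proceed, and the decision rule as written need not register them.

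**Working it through.** **Planned size.** Sampling and Feasibility of recruitment gives the target: "We aim to recruit 90 CYP across the 3 conditions (30 per condition) over the 15-month recruitment period". It gives the rate as follows: "Assuming a recruitment rate of approximately 1.5 cases per month per site, this will be sufficient to recruit to target over the feasibility trial". With 4 sites, 1.5 × 4 × 15 = 90, and 90/3 = 30 per arm under 1:1:1 allocation. The stated figure is reproduced.

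**Lowest single-arm result compatible with a pooled green.** Take the smallest count that meets 80%, then subtract complete results in the other arm or arms.

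| Criterion | Recruited | Needed for green | Lowest possible arm |
|---|---|---|---|
| Retention (three arms) | 90 | 0.8 × 90 = 72 | 72 − 60 = 12 of 30 (40%) |
| Delivery (two arms) | 90 | 0.8 × 60 = 48 | 48 − 30 = 18 of 30 (60%) |
| Retention | 72 (lowest green recruitment) | 0.8 × 72 = 57.6, so 58 | 58 − 48 = 10 of 24 (42%) |
| Delivery | 72 | 0.8 × 48 = 38.4, so 39 | 39 − 24 = 15 of 24 (63%) |

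A case short of the limit: retention of 29, 29 and 14 also gives 72/90 = 80.0%, with one arm at 14/30 = 47%.

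**Receipt of the other treatment.** There is no ceiling. If all 30 PI-alone participants also started APs, criterion iii would still count only CBT sessions and criterion iv, with denominators as randomised, would not include them.

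**All four together.** Recruit 90/90. In the PI-alone arm, retain 12/30, have 18/30 attend at least 6 CBT sessions and have 30/30 start APs. Let the other two arms be complete. Then:

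- recruitment: 90/90 = 100%
- retention: (12 + 30 + 30)/90 = 72/90 = 80%
- PI delivery: (18 + 30)/60 = 48/60 = 80%
- AP delivery: 60/60 = 100%

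Every light is green.

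**Is a misleading green plausible away from the limits?** The true rates below are assumptions, since the protocol gives no arm-specific rates. Counts are binomial, 30 per arm, and the probabilities are exact sums. The weak arm judged alone needs 24/30.

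| Assumed true rate: weak arm, other arm(s) | P(pooled retention green) | P(pooled delivery green) | P(weak arm alone green) |
|---|---|---|---|
| 60%, 90% | 0.56 | 0.22 | 0.017 |
| 60%, 95% | 0.86 | 0.37 | 0.017 |
| 70%, 90% | 0.85 | 0.58 | 0.16 |

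Pooling hides more for retention (three arms) than for delivery (two arms).

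**The case against.** The strongest objection is that the information is not lost. The Data analysis section promises a CONSORT report, numbers recruited to each arm, and counts of drop-out from the allocated interventions and of missing follow-up. The Secondary outcomes section measures AP and PI dose in all groups. The TSC and DMC make a recommendation and nothing makes it automatic, so they could notice a failing arm. By-arm tables may also appear in the SAP. This stands as mitigation. It does not remove the point, because the progression criteria are written out in the protocol, the protocol says the feasibility results are reported overall, and no threshold draws on the arm-level data.

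Several stronger readings might be inferred, and the documents do not support them.

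- *Clinical teams are free to give anything.* The Concomitant therapy section opens with "It would be unethical to restrict the therapeutic options of the clinical teams participating", but ends by making all participants eligible for medications other than APs and psychological therapies other than CBT or FI. Cross-over is still possible, through the transfer provisions and because follow-up continues whatever is later received.
- *Transferred participants would enter the denominator of the treatment they moved to.* The intention-to-treat statement, which covers all randomised participants, largely answers this. The phrase about groups receiving a treatment is loose, but nothing in the protocol directs the other reading.
- *Criterion iv contradicts the prescribing guidance.* Psychiatrists are to be encouraged to continue an AP "for a minimum of 12 weeks, and preferably for 26 weeks". That is an encouraged course and the 6 weeks is a minimum-exposure threshold, so the two can coexist.
- *Criterion iii is defective because it omits family intervention.* Participants without regular family contact do not receive it, so leaving it out of a criterion meant for everyone is a tenable choice.
- *The overall colour should follow the worst arm.* At this size that rule would often penalise a sound trial. If true retention were 85% in every arm (assumed), pooled green has probability 0.93, whereas all three arms reach 24/30 with probability 0.847³ = 0.61.

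**Conclusion.** The point holds, in a limited form. As written, the progression rule can be green on every criterion while one arm has poor retention, delivery in a monotherapy arm is only at the bottom of amber, or a monotherapy arm has largely become combined treatment.

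The size differs by component. Uncounted receipt of the other treatment is the most serious gap, because nothing limits it. Retention is next, with one arm possibly as low as 12/30 (40%). Delivery is the weakest: with equal arms a pooled green cannot conceal an arm below 60%, so a reader should not infer that a red delivery result could be hidden.

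The counts assume equal arms and that criteria iii and iv pool their two arms. The criteria could be read as applying to each group separately, but no text says so and the reporting sentence in Data analysis points to pooling. The limiting cases show what the rule permits and are not forecasts. No clinical transfer rule is judged here. This should be changed, since the PI-alone versus AP-alone contrast is a candidate question for the definitive trial.

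**What to change.** In Data analysis and in Measurement of feasibility success criteria:

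1. Report criteria ii to iv to the TSC and DMC by randomised arm as well as overall, each with a 95% confidence interval.
2. Require the committees to comment on any arm below the green threshold, without an automatic downgrade of the overall colour.
3. Word the denominators of criteria iii and iv as participants randomised to PI or to AP.
4. Add, for each monotherapy arm, the proportion who by 6 months had received the allocated treatment and not the other one, with transfers made under the protocol shown separately.

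The cost is a few table rows. Treatment dose, attendance and follow-up are already to be recorded, and transfers take place under the protocol's own procedure. The drawback is imprecision: at 24/30 the exact (Clopper-Pearson) 95% interval is about 61% to 92%, so an arm just below green may be there by chance. That is why the interval is shown and a comment is asked for in place of a mechanical rule.

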Following informed and written consent, eligible participants will be randomised within 2 working days. Our Clinical Trials Unit will support the development of the randomisation algorithms and the web-based technology. Randomisation will be in the ratio 1:1:1 to the three groups and will be stratified by centre and family contact (since participants who do not have regular contact with their families will not receive the family intervention components of psychological intervention, although they will still be included). Randomisation (at the individual level) will be independent and concealed, using randomised-permuted blocks of random size administered via a study-specific web-based system developed by the CTU. The allocation is made known to the trial manager (to monitor adherence to the randomisation algorithm), the trial administrator and trial therapists by email and SMS text message. The allocation code will be maintained for research assistants until all outcome measures for all participants have been collected.

Protection against bias

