Single blind – assessors will be blind to treatment condition. Blindness will be maintained using a wide range of measures which we have implemented successfully in other single blind trials (EDIE 2; ACTION; FOCUS). These include separate offices for the therapists and research assistants, protocols for answering telephones including reminders for clinicians, participants and family members about the blind, protocols for message taking and secretarial support, separate diaries and pigeon holes and data file security, using passwords and encryption of randomisation information. We will develop a standard operating procedure (SOP) for maintaining, recording and managing blinding, which will outline all of these procedures. This SOP will be reviewed by, and agreed with, our data monitoring committee (DMC)/ trial steering committee (TSC). Each researcher will sign this SOP to confirm they understand and will comply with the blinding procedures. All blind breaks will be recorded by the trial manager and reviewed by the Chief Investigator for patterns in unblindings. There is only one follow-up scheduled during the intervention window (at 3 months). This will reduce the risk of blind breaks occurring because of therapists and RAs crossing paths for visits and it will reduce the opportunity for unblinding to occur because of communication with participants to arrange visits. Maintaining rater blindness to treatment allocation is crucial, and the DMC and TSC will regularly monitor unblindings by each centre, and implement corrective action if necessary. Following eligibility assessment and completion of baseline assessments, participants will be allocated to treatment groups through our web-based randomisation service and the Trial administrator will inform the participants of this decision. All letters to participants and clinicians will contain a standardised statement about the need to maintain the single blinding process. Any accidental unblindings will be recorded. Where possible, we will identify an independent assessor with whom the blind has not been broken to complete subsequent follow-ups, subject to any threats to participant engagement with follow-up. Given each intervention is provided in two arms of this three-arm trial, the blind will also be easier to maintain than in our previous two-arm trials.

Concomitant therapy

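### Family contact, a stratification factor, is described in two ways and is absent from the only stated adjustment; the therapist effect is not limited to the arms that have a trial therapist

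*Protocol*

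**What the plan says.** **Stratification.** The Study Design section names site and family contact as the stratification factors. The Randomisation section agrees ("stratified by centre and family contact") and adds "Randomisation will be in the ratio 1:1:1 to the three groups".

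**Meaning of family contact.** Under Rationale and summary, allocation is "stratified by family contact (i.e. if they are living with their family) and site". Under Randomisation, the reason given for the factor is "since participants who do not have regular contact with their families will not receive the family intervention components".

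**Adjustment and clustering.** The last paragraph of Data analysis opens with "We will measure within trial and also explore the literature regarding the possible effects of clustering by therapist and site" and closes with "We will adjust for site in analyses (therapist will be nested within site) and examine intraclass correlation coefficients". The stated purpose of the ICCs is to help plan how clustering would be handled in a definitive trial. The preceding paragraph defers full pre-specification to a statistical analysis plan, which is not at hand.

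**Who has a therapist.** Protection against bias notes: "Given each intervention is provided in two arms of this three-arm trial". So two of the three arms include PI. The section on qualitative interviews confirms this, because it calls for a risk check with the trial therapist only for participants allocated to a therapy arm. Under Procedures for deterioration, monotherapy participants may move to the combined arm, so some AP-alone participants can gain a therapist later.

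**The concern.** Three features of the text do not fit the design.

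1. A stratification factor has to be classified before allocation. If one site records co-residence and another records regular contact, the strata mean different things, and no later analysis document can undo that. Under Randomisation the same factor is also the stated reason why some participants do not receive the family component.
2. Stratifying on a factor and then leaving it out of the model discards the precision that the stratification bought. Data analysis makes point estimates and 95% confidence intervals the main presentation of outcomes, so their width matters.
3. A therapist level nested within site is undefined, at allocation, for one third of the sample. Leaving those participants out of a treatment comparison would conflict with the stated intention to analyse all randomised participants. Giving them invented clusters would distort the therapist ICC that the definitive trial is meant to draw on.

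**Working it through.** **The Protocol's own figure.** Sampling and Feasibility of recruitment gives 1.5 participants per site per month, 4 sites and 15 months: 1.5 × 4 × 15 = 90, and 90 / 3 = 30 per arm. This reproduces. Hence 60 participants are allocated to arms with PI and 30 to AP alone.

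**Family contact side by side.**

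| Adolescent | Co-residence wording | Regular-contact wording |
|---|---|---|
| Lives with family, in contact | Yes | Yes |
| Lives away, in regular contact | No | Yes |
| Lives away, no regular contact | No | No |

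The second row is the conflict. The documents do not say how many participants fall in it.

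**Leaving family contact out of the model.** Assumed, because the documents give neither: 70–90% have family contact, and its effect on outcome is 0.3–0.8 SD. Simulation: N = 90, three arms, permuted blocks within site by family contact, linear model, 3,000 runs per setting.

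| Model | Coverage of 95% CI | Mean CI width (SD units) |
|---|---|---|
| Site only | 94.6–96.3% | 1.030–1.094 |
| Site and family contact | 94.7–95.4% | 1.025–1.031 |

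Worst case (70% with contact, 0.8 SD): 1.094 / 1.026 = 1.066, about 7% too wide. Mildest case (90%, 0.3 SD): 1.030 / 1.028 = 1.002, practically nothing. As an analytic check, with prevalence p and effect b in residual SDs the width ratio is about √(1 + p(1 − p)b²). In the worst case this is √(1 + 0.7 × 0.3 × 0.64) = √1.1344 = 1.065.

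**Therapist ICC.** Assumed: 4–10 therapists share the 60 PI-arm participants; ANOVA estimator. The misfit coding tested treats the AP-alone participants at each site as one dummy cluster.

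| How the ICC is estimated (true ICC 0.05) | Mean estimate |
|---|---|
| PI-containing arms only | 0.046–0.048 |
| All arms with dummy clusters, no arm difference | 0.031–0.034 |
| Same, unadjusted AP–PI difference 0.3 SD | 0.050–0.053 |
| Same, unadjusted AP–PI difference 0.5 SD | 0.084–0.089 |

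The dummy clusters add a group with no therapist variance, which pulls the estimate down by about one third. If arm is not in the model, a mean difference between AP alone and the other arms enters as between-cluster variance and pushes it up. For scale, the sampling SD of the PI-only estimate is 0.08–0.10, about five times the downward bias of roughly 0.017.

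**Is the therapist effect worth modelling?** For PI alone against AP alone, only one side is clustered. With m participants per therapist in the PI arm, the ratio of true to naive standard error is √{[(1 + (m − 1) × ICC) + 1] / 2}. With 4 therapists, m = 30 / 4 = 7.5. At ICC 0.05 this is √[(1.325 + 1) / 2] = 1.078, and a naive 95% interval covers 93.1%. At ICC 0.10 the ratio is 1.151 and coverage 91.1%. With 8 therapists (m = 3.75) the ratios are 1.034 and 1.067. The Protocol does not plan to ignore therapist, but this shows that dropping the term is not the remedy.

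**The case against.** **Covariates belong in the analysis plan.** The adjustment sentence sits in a paragraph about clustering, gives no covariate list and never says that site is the only covariate. A reader might infer that family contact is excluded; the text does not say so, and the analysis plan may include it. This stands. What remains is that the one adjustment the Protocol states names one of two stratification factors.

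**The nesting is correct.** Therapists do work within sites, the Protocol treats drug-related clustering separately, and a random effect confined to two arms is a standard option. So it does not follow that software must either drop AP-alone participants or invent clusters for them. This also stands. The gap is that the sentence sets no arm restriction.

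**The ICC may not matter much.** A reader might infer that a diluted ICC feeds directly into the definitive sample size and leaves that trial about 14% short. That figure compares design effects at 15 participants per therapist: 1 + 14 × 0.05 = 1.70 against 1 + 14 × 0.033 = 1.47. It needs a dummy coding that the Protocol never states, no unadjusted arm difference, and the largest cluster size in the assumed range. At 6 per therapist the figures are 1.25 and 1.17, about 7%. The Protocol says that the ICCs inform a plan, alongside the literature; the sample size inputs it names are correlations, means and standard deviations. The stronger reading is not supported.

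**The family contact wording.** The Randomisation text can be read as a rationale rather than a formal definition, and the Rationale and summary text says nothing about who receives the family component. So the two places do not set two eligibility rules for that component. They do still describe one stratification factor in two ways.

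**Conclusion.** The point holds as a modest one with three parts.

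- **Firmest:** the two descriptions of family contact conflict for a participant living away but in regular contact. This concerns classification before allocation, so an analysis plan cannot repair it.
- **Sound:** therapist nested within site, with no arm restriction, does not fit a design in which AP-alone participants have no trial therapist at allocation. If they were coded as dummy clusters, the ICC could be too low or too high. The size depends on assumed therapist numbers, ICCs and arm differences, none of which the documents give, and it is small beside the sampling error of the ICC in a trial this size.
- **Weakest:** naming site without family contact. If family contact were in fact left out, intervals would be about 0–7% too wide under the assumed ranges, with coverage at or slightly above nominal.

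No figure in the Protocol is wrong on this point. This is a feasibility trial without planned hypothesis tests, so its conclusions are not threatened.

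**What to change.** 1. Reconcile Rationale and summary with Randomisation to one definition of family contact, and state which definition the randomisation system uses.
2. In Data analysis, state that outcome models adjust for site and for family contact as randomised.
3. State that the therapist effect is a random effect in the PI-containing arms only (a partially nested model), and that the therapist ICC is estimated from those arms and reported with its 95% CI.
4. State how participants who move to the combined arm under Procedures for deterioration are handled in the analysis, including the therapist level for those randomised to AP alone who gain a therapist.

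The cost is a few sentences, one covariate already collected, and one degree of freedom. The partially nested model is a standard mixed-model option.
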